1.0 Objectives

Primary Objective:

- To determine the safety and establish the optimal biologic dose of CYT107.

Secondary objectives:

- To determine the rate of cytomegalovirus (CMV), Epstein-Barr virus (EBV) and BK viral infections in umbilical cord blood stem cell transplantation (CBT) and haploidentical stem cell transplantation (haplo-SCT) patients who receive three doses of IL-7 following engraftment.
- To calculate the OS, PFS and, cumulative incidence of GVHD and cumulative incidence of relapse
- To evaluate the effects of CYT107 on the recovery of T, NK and B cell populations and their functions in vitro; these data will be used to identify the optimal dose to move to a phase II trial.

2.0 Background

2.1 Haploidentical and Cord blood transplantation

Haploidentical stem cell transplantation (haplo-SCT) and umbilical cord blood stem cell transplantation (CBT) are being increasingly used as a source of hematopoietic stem and progenitor cells (HSPCs) for allogeneic stem cell transplant candidates lacking suitable matched donors. Although haplo-SCT and CBT are successful in many patients, their efficacy have been restricted by slow hematopoietic and immunologic reconstitution due to the quantitative and qualitative differences in the composition of the stem cell grafts.¹⁻⁵ While the frequency of HSPCs is greater in CB units, CB grafts contain an average of 1-2 logs fewer total cells compared to peripheral blood (PB) or bone marrow (BM) allografts. Moreover, the vast majority of T, B and dendritic cells in CB grafts are immature,^{6,7} which likely explains the low rates of graft-versus-host disease (GVHD) seen after CBT given the degree of HLA-mismatches typically used.^{8,9} The use of double unrelated CBT (DUCBT) represents an important advance by allowing larger children and adult patients to be transplanted with an acceptable cell dose. In this setting, although two CB units are initially transplanted, only one provides prolonged engraftment and becomes the “dominant” engrafted unit. Yet, even following DUCBT, severe complications related to infections remain a major cause of morbidity and mortality.¹⁵⁻²⁰ Similarly, immune recovery after haplo-SCT also tends to be less robust in comparison with matched grafts, and affects B cells, T cells and their subsets.¹⁻³

[figure not shown]
2.2 Strategies to enhance T-cell reconstitution

Interleukin-(IL-7) has a central role in T-cell development and survival; it enhances thymopoiesis, peripheral T-cell survival and expansion in murine models of allogeneic hematopoietic stem cell transplantation (allo-HSCT).²⁻⁵ Initial trials with recombinant human IL-7 (r-hIL-7) demonstrated an expansion of CD4+ and CD8+ T cells in patients with solid tumors or HIV infection.²¹⁻²⁵ A potential concern with IL-7 in allo-HSCT patients is the stimulation of GVHD. In preclinical mouse models, short courses of IL-7 did not induce GVHD in T-cell depleted bone marrow transplant (TCD-BMT) nor did it aggravate the development of GVHD after adding donor T cells.³ However, IL-7 when given longer and at higher dose to mice after TCD-BMT, did lower the threshold dose of T cells required to induce lethal GVHD.²⁶ In a recent Phase I clinical study of r-hIL-7 in recipients of a T-cell depleted allo-HSCT, investigators at Memorial Sloan Kettering treated 12 patients with escalating doses of IL-7 administered weekly for 3 weeks after the patients had engrafted. They reported that the study drug was well tolerated with only one patient developing acute skin GVHD. At baseline, patients were profoundly lymphopenic. IL-7 induced a doubling in CD4+ and CD8+ T cells with no significant effect on CD4+CD25+FoxP3+ T cells, NK, or B cells. Importantly, they also demonstrated an increase in functional T cell recovery, including viral-specific T cells that recognize CMV. Enhanced T-cell receptor (TCR) diversity was also observed after treatment. The authors concluded that IL-7 can enhance immune recovery after a T cell-depleted allo-HSCT without causing significant GVHD or other serious toxicity.

2.3 Preliminary Studies

Predictors of Non-Relapse Mortality and Overall Survival after CBT. We analyzed the outcome of 108 patients who underwent a DUCBT at our center for predictors of 3-year non-relapse mortality (NRM).²⁸ In univariate analysis, the day 30 absolute lymphocyte counts (ALC30) were treated as dichotomous variables above or below $150 \times 10^6 / \text{L}$ (upper limit of first quartile) and significantly affected NRM. The median (range) of ALC30 was 240 (10-2420) $\times 10^6 / \text{L}$. There was no significant impact of age, sex, disease stage at the time of DUCBT, CMV serostatus, the occurrence of grade II-IV acute GVHD before day 30, total nucleated cell dose (TNC) dose, total CD34 dose, preparative regimen or CB manipulation on NRM. In multivariate analysis, ALC30 (HR = 2.3, $P = 0.01$) emerged as an independent factor strongly associated with NRM. **Figure 1** shows the impact of ALC30 on NRM and OS in all patients. For patients with ALC30 $> 150 \times 10^6 / \text{L}$, overall survival at 3 years was 37% (95% CI 25-49) compared with 25% (95% CI 11-40) for those with counts $\leq 150 \times 10^6 / \text{L}$ ($P = 0.02$). Similarly, ALC30 $> 150 \times 10^6 / \text{L}$ was related to a lower risk of NRM, 42% (95% CI 31-56%) vs 59% (95% CI 44-78%) ($P = 0.01$) in patients with ALC30 $\leq 150 \times 10^6 / \text{L}$. The leading causes of NRM in both the groups (ALC30 ≤ 150 vs. ALC30 > 150) included infections (50% vs. 52%, $P=0.9$) and GVHD (40% vs 30%, $P = 0.5$). Further, there was no significant impact of ALC30 on the rate of grade II-IV aGVHD ($P = 0.4$), disease progression ($P = 0.7$) or progression-free survival ($P = 0.07$) at 2 years.

Figure 1

CBT outcome based on ALC30. Impact of ALC30 \leq or $> 150 \times 10^6/\text{L}$ on (A) OS; (B) NRM.

Figure 2

[figure not shown]

Figure 2. Prolonged T lymphopenia and relative expansion of NK cells and B cells following DUCBT. T (CD3+CD4+ and CD3+CD8+), B (CD19+), and NK (CD56+) cells were prospectively measured by multiparameter flow cytometry on fresh samples; (A) frequencies; (B) absolute numbers ($\times 10^6/\text{L}$) for each immune subset are presented. At baseline and after DUCBT, CD4+ and CD8+ T cells were relatively reduced, whereas early B-cell and NK-cell recovery was evident. Surviving CB transplant recipients demonstrated rebound of CD4+ and CD8+ T cells at later intervals after transplantation. Error bars represent interquartile range.

Lymphocyte subset analysis. In 65 patients for whom peripheral blood (PB) samples had been collected at days +30, +100, +180 or 1 year post-DUCBT, we further characterized immune subset recovery by measuring the frequencies and absolute numbers of CD4+ T cells, CD8+ T cells, CD56+CD3- NK cells, and CD19+ B cells (Figure 2). The absolute number of each cell subset was calculated by multiplying their frequencies as determined by flow cytometry by the absolute lymphocyte number (cells/ μL) obtained from a diagnostic complete blood count performed on the same day. Lymphocyte reconstitution following DUCBT began with a rapid increase in both the absolute number and frequencies of NK cells over baseline norms, and remained increased at the different study intervals, though the percentage of NK cells declined as T-cell counts recovered. T cell reconstitution on the other hand was significantly delayed. CD4+ and CD8+ T cells declined after conditioning and were significantly

reduced by day 30 post-DUCBT. The median absolute number of CD8+ cytotoxic T cells was $6 \times 10^6/L$ (range 0-170) at 30 days and $11 \times 10^6/L$ (range 0-1900) at 100 days post-transplant. The corresponding numbers of CD4+ helper T cells were $4 \times 10^6/L$ (range 0-100) and $22 \times 10^6/L$ (range 0-390), respectively. These results confirm that quantitative T cell recovery is delayed after DUCBT, with an inverted CD4/CD8 T cell ratio, and that this delay in T cell immunity is associated with a preferential rapid reconstitution of non-T lymphoid cells (e.g., NK cells and B cells). Patients who developed acute GVHD had a slower T and B cell recovery (data not shown)²⁹, in keeping with previous reports following allogeneic stem cell transplantation.²⁹

To assess the tempo of functional virus-specific T cell recovery after DUCBT, we stimulated PBMC from 46 transplant recipients with 15-mer overlapping peptides spanning T cell immunogenic antigens from a range of both latent (CMV, EBV, BKV) and community (AdV, Influenza and RSV) viruses as well as to SEB, which was used as a positive control. Prior to transplant the frequency of T cells reactive against SEB was highest (mean 424.5 SFC/2 $\times 10^5$ PBMCs), followed by CMV (mean 258 SFC in 39 seropositive donors), EBV (mean 33 SFC), AdV (mean 17 SFC), BKV (mean 13 SFC), Influenza (mean 8 SFC), and RSV (mean 10 SFC) (**Figure 3**).

Figure 3

[figure not shown]

Figure 3. Virus-specific T cell activity following DUCBT. (A) Frequencies of SEB, BKV (Large T and VP1), AdV (Hexon and Penton) AND CMV (IE1 and pp65)-specific T cells in seropositive and seronegative donors in PB samples collected from patients prior to and post-DUCBT using IFN ELispot as readout. Each symbol represents individual patient and results represent the SFC/2 $\times 10^5$ input cells.

As shown in **Figure 3**, T cell activity against SEB, CMV, EBV, and AdV was delayed for at least 8-9 months following DUCBT (mean 200, 89, 28 and 24 SFC/2 x 10⁵, respectively). All patients developed viral infections/ reactivations post-DUCBT. The most common causes of viral infection included CMV (59%), BKV (20%) and AdV (11%). The majority of these infections occurred within the first 100 days post DUCBT and nearly 50% of patients had infections with multiple viruses.

Haplo-SCT

Immune recovery following haplo-SCT also has been reported to be suboptimal for at least 1 year after stem cell transplantation in comparison with the immune recovery observed following fully matched transplants.³⁵⁻³⁷ Furthermore, the absolute numbers of lymphocyte subsets were much lower after haplo-SCT in comparison with lymphocyte counts seen in normal individuals.³⁵⁻³⁷

Sluggish recovery was reported for CD19⁺ B cells, which according to some studies remained under 100 cells/µL until 180 days after transplantation.³⁷ Poor recovery was also reported in the T cell subsets.³⁵⁻³⁷ In one study, CD4⁺ helper T cells were shown to recover slowly after haplo-SCT and did not reach 400/µL until 12 months after transplantation.³⁷ Although CD8⁺ cytotoxic T cells recovered rapidly after haplo-SCT according to some studies, there was a significant inversion of the CD4:CD8 ratio, which was observed up to 12 months after transplantation.³⁵⁻³⁷ CD4⁻CD8⁻ T cells recovered slowly and did not reach the normal value until 180 days after transplantation.

Slow recovery was also demonstrated in regulatory T cells (CD4⁺CD25⁺).³⁷ Unlike conventional T and B cells, regulatory T cells never reached normal levels at 12 months following haplo-SCT. In addition to absolute numbers and frequencies, immune cell function may be altered following haplo-SCT. For example, one study demonstrated lower numbers of CD28-expressing T cells 1 year following haplo-SCT.³⁷ Moreover, a number of studies have shown that successful immune reconstitution after allo-HSCT significantly correlates with better post-transplant outcomes, including lower infection, relapse and less secondary malignancy rates.^{38,39} Moreover, rapid immune reconstitution specifically following haplo-SCT prognosticated for superior outcomes, suggesting that measures that could “normalize” immune recovery may improve the outcomes for patients following haplo-SCT.⁴⁰

IL-7 and GVHD

Previous studies with infusion of exogenous IL-7 have shown variable effects on GVHD. Whereas Alpdogan et al, using an allogeneic murine model with full MHC class I and II disparity, reported that IL-7 improves immune reconstitution without aggravating GVHD,²⁹ Sinha et al reported increased GVHD in a murine parent into an F1 model.³¹ More recently, a small phase I study, the administration of IL-7 in the setting of T-depleted bone marrow allogeneic transplant appeared to be safe and associated with an increase in functional T cell recovery, including virus-specific T cells that recognize CMV.²⁷ Thus, we propose that treatment with IL-7 after CBT and haplo-SCT will be safe and will not increase the risk of graft-versus-host disease (GVHD) for several reasons: i) the number of infused T cells after CBT is one-log lower than that infused after a bone marrow transplant and two-logs lower than a peripheral blood stem cell transplant (akin to a T-depleted graft); ii) all patients will receive serotherapy with ATG as part of their CBT conditioning and will therefore undergo in vivo T cell depletion; iii) in our CBT population, the median time to acute GVHD grade I-IV is 34 days (manuscript submitted). Administration of CYT107 can be initiated between day 60-180, and all patients with a prior history of aGVHD will be excluded from the study.

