7.3 Trial Conduct

7.3.1 Dose Assignments

Three dose levels of CYT107 will be considered: 5, 10, and 15 mcg/kg, hereafter denoted as dose levels 1, 2, and 3.

Randomization, rather than conventional sequentially adaptive dose selection, is based on the fact that neither $\text{Pr}(\text{DLT})$ nor any biological outcomes are necessarily monotone increasing in

dose of the biological agent IL-7, and also the scientific goal to obtain unbiased comparisons between doses.

A maximum of 21 patients will be randomized among the three IL-7 doses, with the randomization constrained to have exactly 7 patients per dose. Since 2 patients previously have been enrolled and assigned to d=1, a randomization sequence will be provided for assigning doses to the remaining 19 patients, 3 – 21.

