7.3.2 Within-Dose Safety Monitoring Rule

For each dose $d = 1, 2, 3$, denote $p(d) = \Pr(\text{DLT at dose } d)$. Assume that each $p(d)$ follows a beta(.35, .65) prior. Applying the method of Thall et al.⁴¹, enrollment to dose d will be stopped if $\Pr[p(d) > .35 | \text{data}] > .85$. This criterion will be applied continuously starting at $n = 3$, which implies that accrual to d should be stopped if [number of DLTs] / [number of patients evaluated] is greater than or equal to 3/3 or 4/5. To apply this safety rule for each dose to 2 cohorts of size 3 each may or may not require suspension of accrual. For each dose (a) once 1 or more pats in cohort 1 (pats #1,2,3) have “No toxicity” by day 42 of followup, cohort 2 may begin enrollment, and (b) once 2 or more pats in cohorts 1 and 2 combined (pats #1,2,3,4,5,6) have “No toxicity” by day 42 of follow up, the last patient 7 may be enrolled. This rule has the following operating characteristics.

Operating characteristics of the within-dose safety monitoring rule

True $p(\text{DLT} d)$	$\Pr(\text{Stop accrual to } d)$	Sample Size	Quartiles
.35	.163	7, 7, 7	
.55	.497	4, 7, 7	
.60	.601	4, 6, 7	
.65	.607	3, 4, 7	

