7.5.2 Regression Modeling

Bayesian longitudinal regression models⁴² will be fit to the final data on each of the four biological response variables, as defined in section 1, including in each model a parametric function of time and the baseline covariates patient age, type of graft, and disease (AML vs MDS). Preliminary analyses will include a smoothed plot of each longitudinal outcome variable as a function of time.

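### The three numbered reasons for GVHD safety cover cord blood only, yet DLT monitoring, tables, randomisation and models do not separate cord from other transplants

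*Combined protocol and SAP*

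**What the plan says.** Under IL-7 and GVHD, Section 2.3 proposes that "treatment with IL-7 after CBT and haplo-SCT will be safe and will not increase the risk of graft-versus-host disease" and numbers three reasons:

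- (i) T-cell dose: "the number of infused T cells after CBT is one-log lower than that infused after a bone marrow transplant", and two logs lower than in a blood stem cell graft.
- (ii) In vivo T-cell depletion: "all patients will receive serotherapy with ATG as part of their CBT conditioning".
- (iii) Timing: "in our CBT population, the median time to acute GVHD grade I-IV is 34 days".

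Section 2.2 reports that in mice a short course of IL-7 neither caused nor worsened GVHD, whereas a longer, higher-dose course "did lower the threshold dose of T cells required to induce lethal GVHD".

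Section 3.1 admits cord, haploidentical, mismatched unrelated, matched unrelated and matched related recipients, with blood or marrow sources. Neither 3.1 nor 3.2 requires ATG.

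Grade 3 or 4 GVHD is a DLT (7.1.1). In 7.3.2 each dose has a single p(d), and "enrollment to dose d will be stopped if" the posterior probability that p(d) exceeds .35 is above .85. Section 7.3.1 allocates 21 patients "with the randomization constrained to have exactly 7 patients per dose" and names no other constraint. Section 7.5.1 tabulates by dose. Section 7.2 records both type of donor and type of graft; the biological-response models in 7.5.2 use only the latter, which is not defined. Section 7.5.3 selects the optimal dose by the sample mean T-cell percentage at one year.

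**The concern.** The stated reasons and the enrolled population do not match. The claim names haploidentical transplants, and eligibility goes further still, but no numbered reason describes a non-cord graft. By reason (i) itself, marrow and blood grafts carry one to two logs more T cells than cord. It is therefore an open question whether GVHD, and with it the DLT rate, differs by transplant type.

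This has three consequences:

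- **Reporting.** Tables by dose alone cannot answer that question.
- **Monitoring.** Event-free cord patients can hold a pooled p(d) below the stopping limit while non-cord patients at that dose have many DLTs.
- **Dose selection.** With seven patients per dose and no balancing, one dose can by chance receive more of one transplant type, and 7.5.3 compares raw arm means.

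Dilution comes from the single p(d); imbalance comes from the allocation. They are separate problems with separate remedies.

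**Working it through.** **Inputs from the plan (7.3.1, 7.3.2).** Prior beta(.35, .65); limit .35; cut-off .85; looks from n = 3; seven patients per dose.

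**Reproducing the plan's table.** After y DLTs in n patients the posterior is beta(.35 + y, .65 + n − y). Posterior probabilities that p(d) > .35:

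| DLTs / patients | Posterior | Stop? |
|---|---|---|
| 3/3 | .985 | yes |
| 3/4 | .932 | yes |
| 3/5 | .8485 | no |
| 4/5 | .973 | yes |
| 4/6 | .929 | yes |
| 3/7 | .637 | no |

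The bounds are thus 3 DLTs at n = 3–4 and 4 at n = 5–6. An exact recursion that counts stops before patient 7 gives:

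| True rate | Recomputed | Printed |
|---|---|---|
| .35 | .165 | .163 |
| .55 | .502 | .497 |
| .60 | .600 | .601 |
| .65 | .694 | .607 |

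The first three rows agree. The .65 row does not, and it is not used below. The agreement needs 3/4 as a bound; 7.3.2 lists only 3/3 and 4/5.

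**Dilution in single counts.** Three non-cord patients, all with a DLT, give 3/3 and stop the dose. Put two event-free cord patients among the first four at that dose: no earlier look stops, and 3/5 gives .8485 < .85, so enrolment continues. The result is the same under the bounds as listed in 7.3.2. Likewise 3/4 in non-cord patients alone gives .932, while a pooled 3/7 gives .637.

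**Dilution in probability (assumed inputs).** The documents give neither the transplant mix nor DLT rates by type. Assume 10% in cord and 60% in others, with cord share c. Then p = .10c + .60(1 − c). The any-dose figure is 1 − (1 − s)³, where s is the per-dose stop; it assumes the same p at each dose and ignores re-allocation under 7.4.

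| Cord share | p | Per-dose stop | Any-dose stop |
|---|---|---|---|
| 70% | .25 | .06 | .18 |
| 50% | .35 | .165 | .42 |
| 30% | .45 | .32 | .68 |
| 10% | .55 | .50 | .88 |
| 0% | .60 | .60 | .94 |

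With a milder contrast, 25% in cord and 60% in others, the per-dose stop is .165, .274 and .406 at cord shares of 5/7, 1/2 and 2/7.

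**Chance imbalance.** Place K cord patients at random among three arms of seven. The table gives the probability of a difference of three or more cord patients.

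| K | Any two of the three arms | A given pair |
|---|---|---|
| 7 | .38 | .165 |
| 8 | .39 | .18 |
| 9 | .33 | .19 |
| 10 | .42 | .19 |

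**The case against.** **Evidence and safeguards for non-cord patients.** A reader might infer that the plan offers these patients no safety rationale. It does offer some: mouse models, a small phase I study after T-depleted transplant, no dosing before day 60, and exclusions for prior and treated GVHD. This stands, with limits. The phase I evidence is from T-depleted grafts. Section 2.3 says any prior acute GVHD is excluded, while 3.2 excludes only above grade 2; those passages must be reconciled.

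**The mouse signal.** It would be tempting to conclude that the plan's own evidence implies a higher DLT rate in non-cord grafts. Section 2.2 ties that signal to longer, higher-dose IL-7 and reports the opposite for short courses; this trial gives three weekly doses. The documents never call haploidentical grafts T-cell-rich. Much of the DLT composite, such as relapse, fatigue and liver enzymes, is not GVHD. The difference is possible, not shown.

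**The rule is not blind.** A reader might infer that it cannot detect a non-cord excess. It can, with reduced probability, and the any-dose column is well above the per-dose one. The half-and-half case lands exactly on .35 because of the chosen inputs. Toxicity summaries to the IND Office (7.7) and SAE reporting (Section 9) are further detectors, although 7.7 does not ask for a split by transplant type.

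**A separate non-cord stopping rule.** The same criterion on 10 non-cord patients pooled over doses stops with probability .79 at a true rate of .60. Setting that against .165 for one dose is not like for like. Such a rule also stops with probability .26 at .35 (.31 with 15 patients). If one dose has 60% and the others 20%, the mean is (.60 + .20 + .20)/3 = .33 and it fires only about .23 of the time. It is a debatable trade-off.

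**Type of graft.** It may have been meant to capture transplant type. Because it is undefined, one cannot say that haploidentical and matched blood grafts are coded alike, only that nothing prevents it.

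**Conclusion.** The concern holds as a gap between rationale, population and analysis. It rests on text alone that the three numbered reasons are cord-specific, that eligibility is much wider, and that neither the DLT rule, the tables nor the allocation separates transplant types. As planned, the trial cannot report whether its GVHD claim held outside cord blood.

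Dilution follows from the plan's own rule, as the 3/5 example shows, but its size is conditional. Under the assumed 10% and 60% rates it lowers the per-dose stop from .60 to between .06 and .32 at cord shares of 70% to 30%, and only to .50 at 10% cord. The documents do not support a claim that non-cord patients have a higher DLT rate, nor that the rule would miss it.

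The imbalance is a separate, moderate risk: a one-in-three or greater chance (.33 to .42) that some two arms differ by three or more cord patients, if 7 to 10 of 21 are cord. It matters because the dose is chosen on unadjusted means; adjustment in 7.5.2 does not enter 7.5.3.

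**What to change.** - **(a) 7.5.1 and 7.7:** also tabulate DLT, GVHD and infection by transplant type (cord, haploidentical, other donor) over all doses, and show the same split in the toxicity summaries.
- **(b) 7.5.2:** replace the undefined graft covariate with a three-level transplant-type factor built from the donor and graft variables already recorded in 7.2.
- **(c) 7.3.1:** generate the sequence for patients 3 to 21 balanced on cord versus other, within seven per dose, counting the two patients already at dose level 1. This addresses imbalance only, not dilution.
- **(d) 2.3:** limit the claim to the grafts its reasons cover, or add the reasoning for the others.

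The cost is small. The data are already recorded, and the sequence is described as still to be provided. Item (b) adds one parameter if the present graft covariate has two levels; item (c) makes the website set-up slightly more complex. Sample size and the p(d) rule are unchanged.

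A separate non-cord stopping rule is optional. It should be considered only with its operating characteristics shown, including false stops near .35 and the case of a single toxic dose.
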